Title: Low-Dose versus High-Dose Oxytocin Dosing for Induction and Augmentation of Labor:
A Randomized Control Trial

Principle Investigator: [name]

Faculty Supervisor: [name]

Funding: Departmental

IRB number: 22-0240

1. Introduction and Purpose:

There is a nationwide trend of increasing elective induction of labor (IOL). The national rate of induction of labor in 2020 was 31.4%(1) vs. 27.1% in 2013(2). This trend can only be expected to increase further with the implementation of elective 39-week gestation IOL for maternal and neonatal benefits(3) and maternal medical comorbidities. Elective induction of labor is known to take longer than spontaneous labor(3, 4). Additionally, with any labor (induced or spontaneous), the possibility of failure to progress exists. Currently, the leading cause of primary cesarean delivery (CD) is labor dystocia(5, 6), and cesarean deliveries are associated with worse maternal and neonatal outcomes(7). Therefore, it is vital to research safe but effective methods for induction and augmentation of labor. The optimal regimen would result in the highest percentage of vaginal deliveries within the shortest period, with the lowest maternal and neonatal adverse outcomes. Low-dose and high-dose oxytocin protocols for labor have been endorsed by the American College of Obstetricians and Gynecologists (ACOG)(8). Currently, both regimens are considered standard of care at our institution and are being used during induction and augmentation of labor (AOL). Our hypothesis is that high-dose oxytocin results in a shorter time to vaginal delivery compared to low-dose regimen. The goal of this study is to examine the time from initiation of oxytocin titration to delivery in nulliparous individuals undergoing either induction or augmentation of labor.

2. Background:

ACOG has endorsed low-dose and high-dose oxytocin protocols for labor (8). However, no consensus has been reached regarding optimal oxytocin dosing. Previous research has suggested that high-dose oxytocin protocols may decrease total labor duration without an increase in cesarean delivery rates (5, 9-11). The leading concern regarding high-dose protocols revolves around uterine tachysystole, its hypothetical effect on fetal well-being, and a possible increase in cesarean delivery rates for fetal distress.

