4.4 Additional Baseline Procedures

- Routine intrapartum care will be provided by the patient's managing obstetric team.
- A trained and experienced study team will be responsible for all research data abstraction.
- Maternal outcomes will be assessed following delivery.
- The PI and faculty sponsor will review and validate the diagnosis for all subjects identified to have the primary outcomes. If there is uncertainty, a faculty sponsor will review the chart, discuss with the study team, and make a final determination regarding the outcome.
- Data collection forms will be used during these processes and charts will be reviewed up to 30 days postpartum. We will collect demographic data, as well as data related to the patient's intrapartum course, delivery, immediate postpartum period while inpatient, and neonatal outcomes while inpatient.
- Subject's participation will end following delivery.

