4.7 Data Collection

The data collected will not be used for clinical diagnosis or treatment purposes. The data collected will be kept on a password secured UTMB computer. An encrypted USB flash drive will be used to transfer data. The data will be linked to the patient only by the patient's MRN number. This identifier will be needed to access and analyze demographic data. During analysis of the data, all identifiers will be deleted. Data will be collected from the patient's chart and the chart of the neonate. The data collected will include demographics and data needed to assess the primary and secondary outcomes listed below. The data collection sheet is uploaded for review by the IRB. It is imperative that studies involving induction and augmentation of labor and intrapartum care assess the outcomes of the neonate.

Study Summary Flow Diagram

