- Umbilical artery acidemia ($\text{pH} < 7.0$ or base excess $> 12 \text{ mmol/L}$)
- NICU admission rate

- Composite neonatal outcomes (one of more of the following: perinatal death, severe respiratory distress requiring ventilation, neonatal encephalopathy, neonatal seizure, neonatal sepsis, 5-minute APGAR score <7, umbilical artery acidemia, NICU admission)
- Perinatal death

5. Criteria for Inclusion of Subjects:

- Women aged 18-50 years old
- Singleton gestation
- Nulliparous
- Vertex presentation
- Gestational age \geq 37 weeks
- No prior uterine surgery
- Presents for elective or medically indicated induction of labor
- Need for augmentation of labor with oxytocin

These inclusion criteria are a subset of the current inclusion criteria for low-dose and high-dose oxytocin use at our institution.

6. Criteria for Exclusion of Subjects:

- Previous cervical ripening using non-mechanical methods
- Patient unable or unwilling to provide verbal consent
- Contraindications to vaginal delivery
- Fetal demise or life-limiting anomaly
- Allergy to oxytocin
- Non-reassuring fetal heart tracing prior to inclusion
- Maternal pulmonary edema prior to inclusion
- Fetal growth restriction

7. Sources of Research Material:

Research material will be obtained from electronic medical records/charts.

8. Potential Risks:

No significant adverse effects are expected with the use of high-dose or low-dose oxytocin as both methods are the standard of care at UTMB. All enrolled subjects will meet the criteria for both low- and high-dose oxytocin protocols and will not be withheld standard of care as the result of randomization to either group. The most significant rare risks are described under section 8.3 below: uterine tachysystole, blood pressure changes, arrhythmias, and hyponatremia. The patient will undergo inpatient IOL or AOL, so any adverse reaction would be promptly detected and addressed.

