Sample size was calculated based on the determination of superiority. The primary outcome is time in minutes from oxytocin initiation to delivery. For the sample size calculation, based on our prior unpublished data, the primary outcome in the low PIT arm would be 858.6 ± 494.9 mins. Using a difference rate of 25% (High Pit group: 643.9 mins), power of 80% and 2-sided alpha of 0.05,. Final sample size: 170 (85/group). This difference between both methods is clinically significant.

Detailed:

```
power twomeans 858.6 644, sd(494.9) power(0.8)
```

Performing iteration ...

Estimated sample sizes for a two-sample means test

t test assuming sd1 = sd2 = sd
H0: m2 = m1 versus Ha: m2 != m1

Study parameters:

```
alpha = 0.0500
power = 0.8000
delta = -214.6000
m1 = 858.6000
m2 = 644.0000
sd = 494.9000
```

Estimated sample sizes:

```
N = 170
N per group = 85
```

This trial will be registered with Clinical Trials Register (Clinicaltrials.gov) before recruitment is initiated and after IRB approval.

References

6. Obstetric care consensus no. 1: safe prevention of the primary cesarean delivery. *Obstet Gynecol.* 2014;123(3):693-711. doi: 10.1097/01.AOG.0000444441.04111.1d. PubMed PMID: 24553167.

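### Umbilical artery acidemia is defined with the sign of base excess reversed, so the second limb of the definition cannot identify metabolic acidosis

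*Combined protocol and SAP*

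**What the plan says.** Section 4.9 lists umbilical artery acidemia as a secondary outcome with two limbs, either of which is enough: pH below 7.0, "or base excess $> 12" mmol/L.

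The same term appears among the eight components of the composite neonatal outcome ("5-minute APGAR score <7, umbilical artery acidemia, NICU admission"), with no separate definition. The protocol never uses the term base deficit, states no sign convention for base excess, and does not define the item again.

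On how the outcome will be coded, Section 4.4 says: "A trained and experienced study team will be responsible for all research data abstraction". Section 4.7 says: "The data collection sheet is uploaded for review by the IRB". That sheet is not part of the documents available here.

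**The concern.** Base excess is negative when base is lacking, as in metabolic acidosis, and positive when base is in surplus. An acidemia criterion that requires a value above +12 therefore points the wrong way. It excludes the newborns it is meant to find, and it would label a markedly alkalotic newborn acidemic.

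This is a neonatal safety outcome, and the Background section says of the risks: "The leading concern regarding high-dose protocols revolves around uterine tachysystole, its hypothetical effect on fetal well-being". Cord acidemia is one of the more objective measures of that effect.

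Two things could go wrong:

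- **Literal coding.** Newborns with a large base deficit and a pH of 7.0 or more are missed, which costs events and precision.
- **Mixed coding.** Some abstractors read the line as base deficit and others literally, so the outcome is coded inconsistently. Section 4.2 says that blinding is not possible, and no section says that abstractors are masked to arm. Inconsistent coding would therefore not necessarily be balanced between arms.

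**Working it through.** **1. The plan's own figure.** The only calculated figure nearby is the sample size in Section 13. Its inputs are a difference of 858.6 − 644 = 214.6 min, SD 494.9 min, two-sided alpha 0.05 and power 80%. The normal approximation gives n per arm = 2 × (1.960 + 0.842)² × (494.9 / 214.6)² ≈ 83.5, rounded up to 84 (168 in total). The two-sample t test gives 84.46, rounded up to 85 (170 in total), as stated. None of these inputs involves acidemia, so the point leaves N unchanged.

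**2. The definition applied to example cord gases.** The values are illustrative. Three readings are compared: the text as printed, the text with a minus sign restored, and the reading that fits the outcome's name.

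| pH | Base excess (mmol/L) | As printed: pH < 7.0 or BE > 12 | Minus restored: pH < 7.0 or BE > −12 | Sign corrected: pH < 7.0 or BE < −12 |
|---|---|---|---|---|
| 6.98 | −14 | yes | yes (by pH) | yes |
| 7.02 | −14 | **no** | **no** | yes |
| 7.02 | +12.5 | **yes** | **yes** | no |
| 7.25 | −3 | no | **yes** | no |

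As printed, the base limb adds no newborn with metabolic acidosis. Restoring a minus sign makes matters worse, because it would count the unremarkable fourth row. To reach the sensible rule, both the sign and the direction of the inequality would have to be wrong in the text, yet the inequality for pH on the same line is intact. A PDF reading fault is therefore not a credible explanation.

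**3. How many newborns could be missed.** The documents give no cord-gas distribution and do not say that every newborn has a cord gas, so these are ranges on assumptions. Let *s* be the share of newborns with base deficit > 12 and pH ≥ 7.0.

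- Full cord-gas coverage: 170 × *s* for *s* = 0, 1, 2, 3% gives 0, 1.7, 3.4, 5.1 newborns. Per arm the maximum is 85 × 0.03 = 2.55.
- Half coverage: 0 to 5.1 × 0.5 = 2.55 in total.
- Composite, full coverage, if half of those missed have none of the other seven components: 0 to 5.1 × 0.5 = 2.55 in total.

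**4. Effect on the comparison if misses are equal in both arms.** Assume true risks of 6% and 3%, 85 per arm, half of cases missed in each arm and no false positives.

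- Expected events: 85 × 0.06 = 5.1 and 85 × 0.03 = 2.55. After the misses they are 2.55 and 1.275.
- Risk ratio: 5.1 / 2.55 = 2.0 before; 2.55 / 1.275 = 2.0 after.
- Risk difference: 3.0 points before; 1.5 points after.
- SE(log RR) = √(1/a − 1/85 + 1/b − 1/85), with a and b the events in the two arms. Before: √(0.1961 + 0.3922 − 0.0235) = √0.5647 = 0.75. After: √(0.3922 + 0.7843 − 0.0235) = √1.1529 = 1.07.

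**The case against.** The strongest reply is that nobody will apply the line literally. It is headed acidemia and the limb stands beside a low pH, so only base deficit makes sense. Trained staff abstract the data, and Section 9 has the team monitor the validity of abstraction and meet quarterly. The sheet that actually governs coding has not been seen. Cord gases are in the charts, so any miscoding can be undone. The scope is also narrow: one limb of one secondary outcome, with fetal well-being also covered by tachysystole with heart rate changes, Apgar score, NICU admission, perinatal death and the composite. Finally, every share and risk used for the size is assumed, the range starts at zero, and with about 5 against 2.5 expected events a two-fold ratio would be hard to detect even with the right definition.

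Much of this stands. Base deficit was probably intended, the harm is small and recoverable, and there is no evidence that any result has been or will be affected. What does not stand is the conclusion that the text can be left alone. A written outcome definition should not depend on the reader correcting it. The safeguards named do not reach this error: the review of diagnoses by the investigator and faculty sponsor in Section 4.4 is confined to the primary outcome, and checking entries against source documents (Section 9) does not repair a wrong rule applied to a correctly copied value.

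**Conclusion.** The concern holds: the definition is wrong as written, and no other section corrects it. That conclusion follows from the meaning of base excess and needs no assumption about rates.

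The consequence is limited. If the line is applied literally, the stand-alone outcome loses newborns with base deficit > 12 and pH ≥ 7.0, and the composite loses only those of them with no other component. The count cannot be derived from the documents; the assumed shares put it in single figures, possibly zero. With equal misses in both arms the expected risk ratio is roughly unchanged, while the absolute difference shrinks and precision falls. Whether any of this occurs depends on the unseen data collection sheet and on how abstractors read the line. It should be corrected, but it does not threaten the trial's main conclusion.

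**What to change.** In Section 4.9, define umbilical artery acidemia as pH < 7.0 or base deficit > 12 mmol/L (base excess < −12 mmol/L). This keeps the protocol's own cut-off of 12. State that the same definition applies inside the composite neonatal outcome.

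Make the data collection sheet match, and have it record the raw pH and the signed base excess so that the outcome is derived in analysis and not judged at abstraction. If abstraction has begun, check how existing entries were coded and re-derive the outcome from the raw values.

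The cost is a one-line correction and, at most, a recheck of charted cord gases for 170 newborns. Sample size and primary analysis do not change.

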8.1 Randomization risk

There are no foreseen randomization risks as both the study and control group are currently utilized for induction of labor at UTMB.

8.2 Loss of Confidentiality

There is a potential risk of loss of confidentiality any time information is collected. Every effort will be made to keep patient information confidential; however, this cannot be guaranteed.

8.3 Oxytocin infusion

Oxytocin is a naturally present hormone produced by the hypothalamus and released from the posterior lobe of the pituitary gland. It is one the most widely used medications during labor and delivery(14). The half-life of oxytocin ranges from 3-10 minutes(15). Reported maternal side effects include blood pressure changes, arrhythmias, and hyponatremia, however blood pressure changes and arrhythmias have only been noted in case reports(14). Theoretically, higher doses of oxytocin may increase the risk of uterine hyperstimulation(16, 17), with potential increases in fetal distress which may result in cessation of oxytocin administration or higher cesarean delivery rates(18). Increased exposure to oxytocin has also been associated postpartum hemorrhage presumably due to downregulation of uterine oxytocin receptors(17).

Previous studies investigating low- and high-dose oxytocin infusion protocols for induction and augmentation of labor have not shown any increases in maternal or neonatal morbidity with high-dose regimens, including postpartum hemorrhage or drug adverse effects(9-11, 19). Similarly, studies have failed to show an increase in operative vaginal delivery or cesarean delivery with high-dose oxytocin protocols(9, 11). While there is a theoretical increased risk for uterine tachysystole with increased oxytocin exposure, this has not been shown to increase the rate of CD(10, 12). There is inconsistent evidence for the association between high-dose oxytocin and operative vaginal delivery for fetal distress(10, 11). While increments of dosing increases will be different between both arms, the maximum rate of oxytocin infusion will be the same, reducing the risk of overexposure to oxytocin. Continuous fetal monitoring with cardiotocography will be used throughout oxytocin infusion as is standard at UTMB to monitor fetal status and contraction patterns.

9. Subject Safety and Data Monitoring:

The PI and research collaborators will be responsible for monitoring the safety of this study. A yearly report will include participant demographics, expected versus actual recruitment rates, summary of any quality assurance or regulatory issues, and any changes in the protocol because of these issues.

The PIs and collaborators will ensure all aspects of data quality, including monitoring for adherence to consent procedures, inclusion and exclusion criteria, valid abstraction, correct entry, timeliness, and responsiveness to data queries. The team will be meeting every quarter to review procedures and resolve any issues that need to be addressed. A final report will be submitted yearly with every continuation review IRB application.

The data will be collected and stored with the participant deidentified ID code only. The master enrollment log linking patient identifiers with study ID numbers will be kept in a password-protected database on the OB/GYN department's internal server separate from the data, we will be using the Oncore platform as well. Data collection forms will be used. Data on these forms

devoid of personal identifiers will be securely stored at our perinatal research division. The principal investigator or approved research staff will be available to monitor the data and correct any discrepancies based on source documents if needed.

10: Procedures to Maintain Confidentiality:

- The data collected will be indirectly linked to the subject by the patient's medical record number.
- When the subject accepts to participate in the study, a number will be attributed to the patient, and this number will be entered on the data collection sheet.
- The data collected will be transferred to the PI's password-secured UTMB computer, that is stored in a locked room using an USB flash drive
- The study PI will be the only person to have a list with the number designated to each subject and the corresponding patient's MRN number. This list will be kept in a locked cabinet of the PI's locked UTMB office. This identifier is needed to access and analyze demographic data. During the analysis of the data, all identifiers will be deleted.
- Data will not be disclosed to outside persons or entities.

11: Potential Benefits:

It is important to determine the optimal method for IOL and AOL, with the goal of the highest percentage of vaginal deliveries within the shortest period, with the lowest maternal and neonatal adverse outcomes. The optimal regimen would have the lowest exposure to all labor interventions. While low-dose oxytocin protocols may result in less uterine tachysystole and resulting fetal distress, studies have shown an increased length of labor, with associated increased rates of chorioamnionitis, fetal infection, and postpartum hemorrhage(11). Low-dose oxytocin protocols have also been associated with an increase in OVD for labor dystocia(10).

On the other hand, high-dose oxytocin has been associated with a shorter length of labor(5, 9, 10, 19) without an increase in cesarean delivery rates(5, 9, 11). It is also associated with lower incidences of postpartum hemorrhage and chorioamnionitis(9, 11). Though data is currently mixed, high-dose oxytocin protocols may be associated with decreased CD for labor dystocia(5), which would spare women from a major abdominal surgery. A shorter total labor duration would translate to a shorter overall hospital admission, ultimately decreasing overall utilization resources. This could then decrease medical costs for labor and delivery and optimize use of hospital staffing and resources. Thus, it is of benefit both patients and providers to further investigate the optimal methods for induction and augmentation of labor with oxytocin infusions based on evidence rather than physician preference.

13. Statistical analysis/Sample size:

Analysis will be performed by intention-to-treat. Univariable and multivariable analysis will be used to describe the population in the study and to identify potential confounding variables. For this analysis, normality will be tested using Shapiro-Wilk method. Demographics and descriptive statistics will be used to provide a profile of the study sample. Data will be either shown as median +/- IQR or mean +/- SDEV. Bivariate tests such as t test, Pearson's chi square, and

Mann-Whitney tests will be used as indicated to identify any key differences in the profiles of subjects across study conditions. Statistical analyses of primary and secondary outcomes between study groups will be performed by multilevel regression analysis accounting for both confounding variables as well as adjusting for any potential intra class correlation that may arise from the study design.

Sample size calculations

Sample size was calculated based on the determination of superiority. The primary outcome is time in minutes from oxytocin initiation to delivery. For the sample size calculation, based on our prior unpublished data, the primary outcome in the low PIT arm would be 858.6 ± 494.9 mins. Using a difference rate of 25% (High Pit group: 643.9 mins), power of 80% and 2-sided alpha of 0.05,. Final sample size: 170 (85/group). This difference between both methods is clinically significant.

Detailed:

```
power twomeans 858.6 644, sd(494.9) power(0.8)
```

Performing iteration ...

Estimated sample sizes for a two-sample means test

t test assuming sd1 = sd2 = sd
H0: m2 = m1 versus Ha: m2 != m1

Study parameters:

```
alpha = 0.0500
power = 0.8000
delta = -214.6000
m1 = 858.6000
m2 = 644.0000
sd = 494.9000
```

Estimated sample sizes:

```
N = 170
N per group = 85
```

This trial will be registered with Clinical Trials Register (Clinicaltrials.gov) before recruitment is initiated and after IRB approval.

References

6. Obstetric care consensus no. 1: safe prevention of the primary cesarean delivery. *Obstet Gynecol.* 2014;123(3):693-711. doi: 10.1097/01.AOG.0000444441.04111.1d. PubMed PMID: 24553167.
